9. STUDY ASSESSMENTS AND PROCEDURES

9.1 EFFICACY ASSESSMENTS

Inclusion and exclusion criteria will be determined by the electronic pre-screening form and the virtual screening visit, including documentation of concomitant therapies, medical history, and diagnoses, to ensure that participants are diagnosed with MDD, and with low suicide risk.

9.1.1 CLINICAL EVALUATIONS

- 1. The M.I.N.I is a diagnostic tool that will be used during the screening session to confirm diagnosis of MDD.
- 2. The Hamilton Depression Rating Scale 17-item (HDRS17) [15] is a scale is used to determine eligibility and to monitor the severity of the participant's depressive symptoms.
- 3. The C-SSRS (triage form) is a standardized method to assess suicide risk.
- 4. The Maudsley Staging Method is a method of measuring treatment resistance in participants with depression on a scale of 3 to 15 (mild = 3-6; moderate = 7-10; severe=11-15) [16].
- 5. The Altman Self-Rating Mania Scale (ASRM) is a method to detect symptoms of mania and hypomania during the study.

9.1.2 Self-Report Assessments

- 1. The Quick Inventory of Depressive Symptomatology (QIDS) is a 16-item, self-report rating inventory that measures characteristic attitudes and symptoms of depression and will be used to monitor the severity of the patient's depression throughout the study.
- 2. The Quality of Life Enjoyment and Satisfaction Questionnaire, short form (Q-LES-Q-SF)[17] is a self-report questionnaire that assesses quality of life.
- 3. Stimulation side-effect questionnaires are administered after every stimulation session. Systematic query of side effects across all major organ systems is administered at D5.

9.1.3 HIGH-DENSITY (HD) EEG

Eyes-open and eyes-closed resting state recordings will be collected before and after CL-tACS on D1 and during the FU2 visit to measure changes in alpha oscillations. High-Density (HD)-EEG will be performed using a HydroCel Geodesic Sensor Net (128 channel) with a Net Amps 400 series amplifier (Magstim EGI, Eugene, OR, USA) with whole scalp coverage.

9.2 SAFETY AND OTHER ASSESSMENTS

9.2.1 SUICIDAL IDEATIONS AND SUICIDAL BEHAVIOR

Only participants deemed at low suicide risk based on the C-SSRS (ideation allowed, however intent, plan or attempt excluded) are enrolled in this study. The C-SSRS [14] will be administered by trained research personnel at screening and the follow-up session to thoroughly assess suicide risk. In addition, the answers to suicide-related questions on the HRDS-17 and on the QIDS will be monitored. Based on these sources of information, clinical personnel will decide if an acute assessment is required. Acute assessment may include facilitating contact of the participant with their psychiatrist or primary care physician to establish a plan for safety, continued care, and follow-up. If the participant does not have an established provider, [name] or [name] will assist in establishing a care plan. If at any point during the assessment, the participant is deemed an imminent risk of harm to self or others, study personnel will enlist the aid of security at the facility or first responders to ensure that the participant is safely escorted to the Emergency Department for further care. [name] and/or [name] will decide if participation should be stopped after the acute assessment. If the participant is hospitalized, their participation will end.

9.2.2 DEVELOPMENT OF MANIA

The Altman Self-Rating Mania Scale (ASRM) was designed to assess the severity of manic symptoms at enrolment, with the ability to track changes over the duration of participation. When undergoing treatment for depression, a possible side effect (as inferred from clinical trials with antidepressant medications) is to alter levels of serotonin, potentially associated with mania [18], [19]. Although we do not expect such an event to occur since there are no reports of inducing mania by tACS and we are not using a medication that targets serotonin levels, we will be conducting this assessment as a precautionary measure. If a participant develops any sign of mania (ASRM > 6), [name] or [name] will conduct an acute assessment to determine if the participant is experiencing mania. If this occurs during the week of stimulation, participation in the study will be stopped and their primary mental health care provider or family physician will be contacted. In the case that they do not see anyone for their mental health concerns, [name] or [name] will assist in creating a medical care plan.

9.2.3 Adverse Event Assessment

A self-report form of sensory experiences associated with stimulation and side-effects will be administered at D1-D5. In addition, a structured interview probing for the experience of adverse events will be administered at D5. [name] or [name] will use the completed interview to assess the severity of the adverse event and its potential relationship to the study intervention.

9.3 Adverse Events and Serious Adverse Events

9.3.1 DEFINITION OF ADVERSE EVENTS (AE)

Adverse event means any untoward medical occurrence associated with the use of an intervention in humans, whether considered intervention-related (21 CFR 312.32 (a)).

9.3.2 DEFINITION OF SERIOUS ADVERSE EVENTS (SAE)

An adverse event (AE) or suspected adverse reaction is considered "serious" if, in the view of the investigator, it results in any of the following outcomes: death, a life-threatening adverse event, inpatient hospitalization or prolongation of existing hospitalization, a persistent or significant incapacity or substantial disruption of the ability to conduct normal life functions, or a congenital anomaly/birth defect. Important medical events that may not result in death, be life-threatening, or require hospitalization may be considered serious when, based upon appropriate medical judgment, they may jeopardize the participant and may require medical or surgical intervention to prevent one of the outcomes listed in this definition.

9.3.3 CLASSIFICATION OF AN ADVERSE EVENT

9.3.3.1 SEVERITY OF EVENT

All adverse events (AEs) will be assessed by the principal investigator and/or co-investigator(s) using the following guidelines:

- **Mild** Events require minimal or no treatment and do not interfere with the participant's daily activities.
- **Moderate** Events result in a low level of inconvenience or concern with the therapeutic measures. Moderate events may cause some interference with functioning.
- Severe Events interrupt a participant's usual daily activity and may require systemic drug therapy or other treatment. Severe events are usually potentially life-threatening or incapacitating. Of note, the term "severe" does not necessarily equate to "serious".

9.3.3.2 RELATIONSHIP TO STUDY INTERVENTION

All adverse events (AEs) must have their relationship to study intervention assessed by the principal investigator and co-investigator(s) who examines and evaluates the participant based on temporal relationship and their clinical judgment. The degree of certainty about causality will be graded using the categories below. In a clinical trial, the study product must always be suspect.

- Definitely Related There is clear evidence to suggest a causal relationship, and other possible contributing factors can be ruled out. The clinical event, including an abnormal laboratory test result, occurs in a plausible time relationship to study intervention administration and cannot be explained by concurrent disease or other drugs or chemicals. The response to withdrawal of the study intervention (dechallenge) should be clinically plausible. The event must be pharmacologically or phenomenologically definitive, with use of a satisfactory rechallenge procedure if necessary.
- **Probably Related** There is evidence to suggest a causal relationship, and the influence of other factors is unlikely. The clinical event, including an abnormal laboratory test result, occurs within a reasonable time after administration of the study intervention, is unlikely to be attributed to concurrent disease or other drugs or chemicals, and follows a clinically reasonable response on withdrawal (dechallenge). Rechallenge information is not required to fulfill this definition.
- **Potentially Related** There is some evidence to suggest a causal relationship (e.g., the event occurred within a reasonable time after administration of the trial medication). However, other factors may have contributed to the event (e.g., the participant's clinical condition, other concomitant events). Although an AE may rate only as "possibly related" soon after discovery, it can be flagged as requiring more information and later be upgraded to "probably related" or "definitely related", as appropriate.
- Unlikely to be related A clinical event, including an abnormal laboratory test result, whose temporal relationship to study intervention administration makes a causal relationship improbable (e.g., the event did not occur within a reasonable time after administration of the study intervention) and in which other drugs or chemicals or underlying disease provides plausible explanations (e.g., the participant's clinical condition, other concomitant treatments).
- Not Related The AE is completely independent of study intervention administration, and/or evidence exists that the event is definitely related to another etiology. There must be an alternative, definitive etiology documented by the clinician.

9.3.3.3 EXPECTEDNESS

The principal investigator ([name]), with input from the co-investigator ([name]) when necessary, will determine whether an adverse event (AE) is expected or unexpected in this population. The co-investigators ([name] and [name]) are experts in non-invasive brain stimulation and will provide their expert opinion regarding this as well. An AE will be considered unexpected if the nature, severity, or frequency of the event is not consistent with the risk information previously described for the study intervention.

9.3.4 TIME PERIOD AND FREQUENCY FOR EVENT ASSESSMENT AND FOLLOW-UP

The occurrence of an adverse event (AE) or serious adverse event (SAE) may come to the attention of study personnel during study visits, or the study participant may report AE or SAEs outside of a scheduled study visit. All AEs including local and systemic reactions not meeting the criteria for SAEs will be captured on the appropriate case report form (CRF). Information to be collected includes event description, time of onset, clinician's assessment of severity, relationship to study product (assessed only by those with the training and authority to make a diagnosis), and time of resolution/stabilization of the event. All AEs occurring while on study must be documented appropriately regardless of relationship. All AEs will be followed to adequate resolution. Any medical condition that is present at the time that the participant is screened will be considered as baseline and not reported as an AE. However, if the study participant's condition deteriorates at any time during the study, it will be recorded as an AE. Changes in the severity of an AE will be documented to allow an assessment of the duration of the event at each level of severity to be performed. AEs characterized as intermittent require documentation of onset and duration of each episode.

Research personnel will record all reportable events with start dates occurring any time after informed consent is obtained until 7 (for non-serious AEs) or 30 days (for SAEs) after the last day of study participation. Events will be followed for outcome information until resolution or stabilization. All AEs including local and systemic reactions not meeting the criteria for SAEs will be captured on the appropriate case report form (CRF). Information to be collected includes event description, time of onset, clinician's assessment of severity, relationship to study product (assessed only by those with the training and authority to make a diagnosis), and time of resolution/stabilization of the event. All AEs occurring while on study must be documented appropriately regardless of relationship. All AEs will be followed to adequate resolution.

Of note, common experiences associated with the application of low-amplitude electric current to the scalp such as phosphenes and tingling sensation are captured with a daily questionnaire. These events are only considered AEs if they are reported as bothersome or untoward by the participant.

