Risk of Injury and Discomfort: The side effects of tACS are mild and transient; in fact, low intensity transcranial current stimulation, such as tACS, has been used for several years without any report of serious side effects [12]. Furthermore, this stimulation mode has nothing to do with electroconvulsive therapy that applies many orders of magnitude higher stimulation current. Rather, transcranial current stimulation is so weak that it does not cause super-threshold activation of neurons [13]. However, tACS does have some mild side effects, such as transient mild tingling, burning, or itching under the electrode sites. [6]. To monitor these mild side effects, we will be administering a stimulation questionnaire after each stimulation session to determine whether these effects were experienced and at what intensity. Research personnel are present during the full experiment.

Patients with MDD have an about 20 times higher rate of suicide than average. We have no evidence that our treatment paradigms will in any way increase this likelihood. Rather, active engagement in a clinical trial may offer hope and structure to the participants. Regardless, participants with high suicide risk (intent or plan) will not be included in this study. If an enrolled participant shows signs of suicide risks that were not apparent during enrollment, a referral to UNC Psychiatry will be made. [name], Co-I, will facilitate this process.

We will be using the Columbia Suicide Severity Rating Scale (C-SSRS, triage form) [14] to determine intent for suicide during D1. Inclusion criteria state that the participant must be low suicide risk and that

potential participants with an above "low risk" designation will not be eligible for the study. In the event that suicide risk increases during participation in the study, the participant will be asked to stop the study. The participant will be provided with a referral to UNC Department of Psychiatry, and their mental health care or family medical doctor will be contacted.

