10.4.4 SAFETY ANALYSES

As discussed in *Section 8.2, Safety and Other Assessments* safety will be assessed with the C-SSRS, an adverse effects questionnaire, and the Altman Self-Rating Mania Scale (ASRM).

The C-SSRS will be used to assess suicide risk. If a participant's responses have an elevated risk, the participant will be contacted, and an acute assessment will be completed if deemed necessary by Dr.

[name] or [name] (as described above). Any verified increases in suicidal ideation will be described in counts/percentages. The C-SSRS is administered at the screening visit and at the 14-day follow up.

The stimulation questionnaire will be administered at D1-D5 after stimulation. This questionnaire solicits ratings of 11 possible sensory experiences ("flickering light") and adverse effects ("scalp pain") associated with electrical stimulation, on a scale of 0 (absent), 1 (low), 2(medium), and 3 (high). Intensity of sensory experiences and adverse effects will be described with mean and standard deviation.

The Altman Self-Rating Mania Scale (ASRM) will be used to assess any development of mania over the course of treatment. A ASRM score of greater than 6 indicates the possible development of a manic episode. Any participant who scores greater than 6 on the ASRM will be assessed by [name] or [name]. Any verified manic episode will be described in counts/percentages.

The Adverse Events Structured Interview will be administered by research personnel at D5 and whenever a participant spontaneously reports a potential AE during trial participation. This interview solicits open-ended descriptions of 13 possible adverse effects a participant may experience in any clinical trial as well as one question of 'any other experiences'. Responses will be reviewed by the clinician and rated as described in **Section 8.3.** Severity per adverse effect will be described with mean and standard deviation.

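### Bother decides whether a stimulation sensation is an AE, but the daily form as described rates only intensity, and mean and SD cannot show how many participants had strong effects

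*Combined protocol and SAP*

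**What the plan says.** Section 9.3.4 says that common scalp-stimulation experiences "such as phosphenes and tingling sensation are captured with a daily questionnaire", and then sets the rule for AE status: "These events are only considered AEs if they are reported as bothersome or untoward by the participant".

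The daily form is described in two places. Section 3.3.1 gives its purpose: "to determine whether these effects were experienced and at what intensity". Section 10.4.4 gives its content: "This questionnaire solicits ratings of 11 possible sensory experiences" together with adverse effects, each scored "on a scale of 0 (absent), 1 (low), 2(medium), and 3 (high"). Flickering light is its example of a sensation and scalp pain its example of an adverse effect. The planned summary is: "Intensity of sensory experiences and adverse effects will be described with mean and standard deviation".

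There is a second instrument, the Adverse Events Structured Interview, "administered by research personnel at D5 and whenever a participant spontaneously reports a potential AE". Section 10.4.4 adds: "This interview solicits open-ended descriptions of 13 possible adverse effects a participant may experience in any clinical trial", plus one catch-all question. A clinician reviews and rates the answers, and severity per effect is again summarised by mean and SD. Section 9.2.3 has the clinician judge severity and relatedness from the completed interview. It does not name the daily form as an input to that judgement.

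**The concern.** The rule that decides AE status needs one piece of information, whether the participant was bothered. The instrument assigned to these sensations is not described as collecting it. Intensity is not the same thing: a strong phosphene may trouble nobody, and a moderate itch may trouble someone a good deal. With no bother item and no score that prompts review, the rule cannot be applied from the daily form on the day.

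The summary adds a second problem. Tingling, burning and itching under the electrodes are the side effects that section 3.3.1 itself expects, so a pilot should be able to say how many people had them strongly and how many found them bothersome. A mean and SD of a 0-3 score answer neither question.

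**Working it through.** **Step 1. Rule against instrument.** The plan states no figure on this point, so the first check is of the text.

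| Needed under 9.3.4 | Daily form as described (3.3.1, 10.4.4) |
|---|---|
| Participant finds the sensation bothersome or untoward | Not described |
| A step from the rating to AE review and the CRF | None stated; no score is a trigger |
| Onset, clinician's severity, relatedness and resolution for each AE | Item and participant-rated intensity on a given day |

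**Step 2. What the D5 interview adds.** It asks about side effects directly, it has a catch-all question, and a clinician reviews it. Three limits follow from the text:

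- The schedule in 2.1 places it once, at D5. Effects on D1-D4 reach it through recall, or earlier if the participant speaks up.
- It is described as covering effects that could occur in any trial, and in 9.1.2 as a query across organ systems. It is not described as revisiting the 11 stimulation items.
- For participants who stop stimulation early, 8.1 says in general that remaining procedures should be completed, but the contacts it names are FU1 and FU2. The interview is not named.

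**Step 3. What mean and SD can show.** The documents give no observed ratings, so the scores here are assumed. Take one item at one session, with k of N participants scoring 3 and the rest 0. N is 28 (target for analysis) or 35 (maximum consented), from 10.2 and 8.2.

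Mean = 3k/N. SD = √[(9k − 9k²/N)/(N − 1)].

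For k = 3 and N = 28: mean = 9/28 = 0.32; SD = √[(27 − 81/28)/27] = √0.893 = 0.94.

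| k | N = 28: mean (SD) | count | N = 35: mean (SD) | count |
|---|---|---|---|---|
| 1 | 0.11 (0.57) | 3.6% | 0.09 (0.51) | 2.9% |
| 3 | 0.32 (0.94) | 10.7% | 0.26 (0.85) | 8.6% |
| 5 | 0.54 (1.17) | 17.9% | 0.43 (1.07) | 14.3% |

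If the five sessions were pooled, which 10.4.4 neither states nor excludes, one participant scoring 3 at one session would contribute 3/(5 × 28) = 0.02 to the mean.

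**Step 4. Can the count be recovered from mean and SD together?** Two patterns at N = 28:

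- A: 19 score 0 and 9 score 2. Sum = 18; sum of squares = 9 × 4 = 36.
- B: 16 score 0, 9 score 1 and 3 score 3. Sum = 9 + 9 = 18; sum of squares = 9 + 27 = 36.

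Both give mean = 18/28 = 0.64 and SD = √[(36 − 18²/28)/27] = √0.905 = 0.95. Pattern A has no participant at the maximum and pattern B has three, so the planned summary cannot tell them apart.

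**Step 5. Other counts.** In 10.4.4, counts and percentages are planned for verified increases in suicidal ideation and verified manic episodes. None is stated for participants with a local effect or with any AE. The general rule in 10.4.1 gives counts for categorical data, but 10.4.4 specifically treats these ratings as continuous.

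**The case against.** The strongest reply is that the plan does ask about adverse effects. The D5 interview is solicited, has a catch-all question and goes to a clinician. It is repeated when a participant reports something spontaneously. Staff are present at every session (7.1.2), and 9.3.4 lets AEs come to light at any visit and sends local reactions to the CRF. This stands, and it rules out several stronger readings that a reader might infer:

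- *The ratings have no way into the AE record, or an effect counts only if the participant volunteers it.* The interview is a solicited route. What is missing is a stated direct step from the daily form.
- *The AE rate will be too low.* The documents support only that some effects may be missed. They give no ratings and no comparator rate.
- *A maximum score for scalp pain would go unrecorded.* The exemption in 9.3.4 names phosphenes and tingling as examples, while 10.4.4 calls scalp pain an adverse effect. Whether the exemption covers it is not stated.
- *Rapport with staff will suppress complaints.* Section 6.5 gives the opposite purpose: participants should feel able to speak openly.

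It is also fair that counting expected, transient sensations as AEs only when they are untoward fits the AE definition in 9.3.1, so the rule itself is defensible. The form is not reproduced in the documents, so a bother item or free-text field may exist, and the D5 Treatment Experience Questionnaire is listed without its content. Finally, an SD about three times the mean does hint at a skewed minority. Step 4 shows that it still does not give the number.

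**Conclusion.** The concern holds in a limited form. As described, the daily form does not collect the attribute on which 9.3.4 makes AE status depend, and no score is stated to prompt review. The D5 interview and spontaneous reports narrow the gap but do not close it. The exposure is greatest for D1-D4 effects no longer recalled at D5, and for participants who stop before D5. The number of AEs that might be missed cannot be estimated from the documents.

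The reporting part does not depend on whether the form has an unlisted bother item. Mean and SD cannot show how many participants had strong effects: 3 of 28 at the maximum can appear as 0.32 (SD 0.94), and 0.64 (SD 0.95) fits either none or three at the maximum. These scores are assumed, for one item at one session.

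This is a worthwhile, inexpensive improvement to safety capture and reporting. It does not touch the primary endpoint.

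**What to change.** 1. Add one question to the daily D1-D5 form: *Was any of these bothersome or untoward? If yes, which?*
2. State in 9.3.4 that each yes goes to AE review and the CRF, with severity graded under 9.3.3.1. State also whether items that 10.4.4 calls adverse effects, such as scalp pain, fall under the bother rule.
3. In 10.4.4, report the number and percentage of participants with at least one such AE, and, for each item, the number and percentage at each worst score. Keep the mean and SD alongside.

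If the form already has such an item, say so in 9.3.4 and make only the reporting change.

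The cost is one tick-box on an existing form and a few lines of text and tables. The reported AE count will probably rise, and the report should explain that the daily question contributes to it.
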